4.6.1.3. One-Level I-GAIS Responder for Either Buttock or Either Thigh

One-level I-GAIS Responder for either buttock is defined as any buttock-treated subject with an improved (+1, +2 or +3) score on the I-GAIS for at least one buttock at an evaluation visit.

One-level I-GAIS Responder for either thigh is defined as any thigh-treated subject with an improved (+1, +2 or +3) score on I-GAIS for at least one thigh at an evaluation visit.

4.6.2. CR-PCSS – Buttock

4.6.2.1. CR-PCSS-Buttock Ratings

To assess the effect of CCH treatment on buttock cellulite in adult females, the mean change from baseline (Screening) in CR-PCSS will be determined for each buttock on Day 22, Day 43, Day 90, and Day 180 Visits as a secondary efficacy endpoint.

4.6.3. Body-Q Appraisal of Cellulite

4.6.3.1. Individual Item Ratings

To assess the subject satisfaction with CCH treatment of buttock or thigh cellulite in adult females, the Body-Q Appraisal of Cellulite score for each of the 11 questions will be summarized for treated buttock or thigh subjects at Day 90 and Day 180 Visits.

To assess the improvement in subject satisfaction with CCH treatment of buttock or thigh cellulite in adult females, change from baseline in the Body-Q Appraisal of Cellulite score greater than or equal to +1 for each of the 11 questions will be summarized for treated buttock or thigh subjects at Day 90 and Day 180 Visits.

4.6.3.2. Total Scores

Total score will be calculated for a subject at all visits. In case of missing responses for a subject, total score will be imputed as explained in Section 6.3. Mean change from baseline (Screening) in Body-Q Appraisal of Cellulite for total score will be assessed for treated buttock or thigh subjects at Day 90 and Day 180 Visits.

Higher scores reflect a better outcome.

4.6.3.3. RASCH Transformed Score

Body-Q™ Appraisal of Cellulite RASCH Transformed Score is the total score converted into a score from 0 (worst) to 100 (best) based on responses for all 11 questions for a subject (Table 14). For a subject the minimum total score will be 11 and the maximum total score will be 44.

Mean change from baseline (Screening) in Body-Q Appraisal of Cellulite RASCH transformed score will be assessed for treated buttock or thigh subjects at Day 90 and Day 180 Visits.

Table 14: BODY-Q- Appraisal of Cellulite Conversion Table

Sum Score	Equivalent RASCH Transformed Score (0-100)
11	0
12	10
13	15
14	19
15	22
16	25
17	28
18	30
19	32
20	35
21	37

Table 14: BODY-Q- Appraisal of Cellulite Conversion Table (Continued)

Sum Score	Equivalent RASCH Transformed Score (0-100)
22	39
23	40
24	42
25	44
26	46
27	48
28	50
29	52
30	54
31	56
32	58
33	60
34	63
35	65
36	68
37	70
38	73
39	76
40	79
41	83
42	87
43	92
44	100

4.6.4.

[REDACTED]

4.6.5.

[REDACTED]

[figure not shown]
[REDACTED]

[REDACTED]

[REDACTED]

4.6.5.4.

[REDACTED]

4.6.6. Scores for Each Question on [REDACTED]

Scores for each question and total score on the [REDACTED] will be summarized at Day 43. Total score will be sum of scores from two individual questions.

4.6.7. Scores for Each Question on [REDACTED]

Scores for each question and total score on the [REDACTED] will be summarized at Day 90. Total score will be sum of scores from two individual questions.

4.7. Safety Parameters

4.7.1. Adverse Events

AE verbatim terms as reported by the investigator will be mapped to System Organ Class (SOC) and Preferred Term (PT) using the Medical Dictionary for Regulatory Activities (MedDRA).

4.7.1.1. Treatment Emergent Adverse Events

TEAEs are defined as any AEs that occur or worsen (increase in severity) on the same day or after the study drug administration on Day 1.

Refer to Section 6.3.1.1 to identify TEAE status when start date of an AE is unknown.

4.7.1.2. Intensity of Adverse Events

Intensity (or severity) of AEs will be graded as “Mild”, “Moderate” or “Severe”. For AEs with missing severity, the most severe assessment will be imputed for analyses, following worst case principle. If the intensity of an AE changes, then the most severe intensity during the continuous episode will be recorded.

4.7.1.3. Relationship to Study Drug

The causal relationship with study drug will be classified by the investigator and will be reported as follows:

- Not related.
- Unlikely related.
- Possibly related.
- Probably related.

Related adverse events are AEs with the relationship described by the investigator as “probably related” or “possibly related”. “Not related” or “Unlikely related” causality assessments are considered as not related.

Any missing relationship of an AE to study drug will be considered as related to study drug for the analyses, following worst case principle.

4.7.2. Vital Signs and Clinical Laboratories

4.7.2.1. Potentially Clinically Important Laboratory Values

Sponsor determined potentially clinically important (PCI) laboratory values are presented in Table 15 below:

Table 15: Potentially Clinically Important Laboratory Criteria

Parameter	PCI Low: Less than or equal to	PCI High: Greater than or equal to
Hemoglobin (g/L)	100	190
Hematocrit (%)	30	60
Platelets (10 ⁹ /L)	100	650
ALT (U/L)		3×ULN
AST (U/L)		3×ULN
Creatinine (µmol/L)		300
BUN (mmol/L)		12

ALT=Alanine transaminase; AST=Aspartate transaminase; BUN=Blood urea nitrogen; ULN=Upper limit of normal.

4.7.2.2. Potentially Clinically Important Vital Sign Values

Vital sign values are PCI if they meet both the observed value criteria and the change from baseline criteria. The sponsor determined PCI vital sign values are presented in Table 16 below:

Table 16: Potentially Clinically Important Vital Sign Criteria

Parameter	PCI Low	PCI High
Systolic blood pressure	≤90 mmHg and decrease ≥20 mmHg from baseline	≥180 mmHg and increase ≥20 mm Hg from baseline
Diastolic blood pressure	≤50 mmHg and decrease ≥15 mmHg from baseline	≥105 mmHg and increase ≥15 mmHg from baseline
Pulse rate	≤50 bpm and decrease ≥15 bpm from baseline	≥120 bpm and increase ≥15 bpm from baseline
Respiratory rate	≤8 brpm and decrease ≥7 brpm from baseline	≥25 brpm and increase ≥7 brpm from baseline
Temperature		≥38.3°C and increase ≥1.1°C from baseline

bpm=Beats per minute; brpm=Breaths per minute.

4.8. Other Safety Parameters

4.8.1. Immunogenicity

Serum samples will be collected and will be tested for binding anti-AUX-I and anti-AUX-II antibodies. When immunogenicity samples are required on Day 1, the samples will be collected prior to study treatment administration. The samples also will be tested for neutralizing antibodies at times to be determined by the sponsor.

4.8.2. Body Dysmorphic Disorder Questionnaire

Subject will be classified as Body Dysmorphic Disorder (BDD) if subject answered Yes to both parts of Q1, answered Yes to any one of the subpart questions for Q3 and answered >1 hour a day for Q4. BDDQ responses and BDD subjects will be summarized at Day 180.

5. ANALYSIS POPULATIONS

The study will use the following analysis populations for data summaries.

Table 17: Analysis Populations

Population	Definition	Displays
Safety Population	The Safety Population will include all subjects who receive at least 1 injection of study medication.	All demographic and baseline characteristics as well as safety parameters will be summarized based on this population.
Evaluable Population	The Evaluable Population will include all subjects who receive at least 1 injection of study medication and have at least 1 I-GAIS evaluation.	All efficacy analysis will be based on this population.

6. STATISTICAL METHODS

6.1. General Methodology

All statistical tests, summary tables and data listings will be prepared using SAS version 9.3 or higher.

All statistical tests will be performed with a significance level of $\alpha=0.05$, unless specified otherwise and will be supported by presenting estimates and 95% confidence intervals (CI).

Continuous data will be summarized using descriptive statistics. Discrete data will be summarized using frequency counts and percentages. The denominator will be based on the number of evaluable subjects in the appropriate population.

For the purpose of display, the summary results will be rounded as follows:

- Minimum and maximum: same number of decimal places as the raw data.
- Mean and Median: one decimal place more than the raw data.
- Standard deviation (SD): Two decimal places more than the raw data.
- Percentages will be displayed with one decimal place precision.

For categorical variables with missing values, a category documenting the frequency of missing values will be displayed in the summary tables.

Summary tables, subject listings, graphs and any supportive SAS output will include footnotes that will indicate:

- Date of data extraction.
- Date and time of output generation.
- SAS program name, including the path, which generated the output.

When calculating percentages, the denominator will be based on the number of subjects with non-missing values. If the denominator is expected to change over time, then the denominator used to calculate the percentage will be based on the number of subjects with non-missing values at each visit. Any subject removed from an analysis will be noted at the bottom of the table along with the reason the subject was removed.

Empty summary tables will be presented with a note stating that “No Subjects Met Criteria”.

Subject listings of all data from the eCRFs as well as any derived variables will be presented.

6.2. Derived Variables

Table 18 defines the derived variables for study parameters:

Table 18: Derived Variables and Definition

Variable	Definition
Age Group	18 – <35 years 35 – <45 years 45 – <60 years
Height (cm)	If height is recorded in inches, then height is equal to the recorded value multiplied by 2.54 and then rounded to 1 decimal place.
Weight (kg)	If weight is recorded in pounds, then weight is equal to the recorded value multiplied by 0.454 and then rounded to 1 decimal place.
Body Mass Index(BMI)	BMI will be computed using height measured at screening and body weight measured at respective visits as, $BMI (kg/m^2) = Weight (kg) / Height (m)^2$
Relative Day	The day of first injection of study drug will be considered as relative Day 1.
Study Day (for assessment on or after Day 1)	Study Day will be computed as: Date of Assessment – Date of Day 1 + 1
Study Day (for assessment before Day 1)	Study Day will be computed as: Date of Assessment – Date of Day 1
Baseline	Baseline is defined as the last non-missing measurement/assessment prior to the first dose of study drug. For vital signs, the baseline will be the Day 1 pre-dose values. For clinical laboratories this will be the screening value. The assessments made in unscheduled visits will be considered in calculation of baseline, if the unscheduled assessment is the closest value preceding the first dose of study drug.
Change from Baseline	Change from baseline will be derived as: post-baseline visit/time point value – the baseline value.
Last Date in Study	Last date in study is defined as: 
 • The date of Day 180 if the subject completes the study. • The date of early termination visit if the subject is terminated early from study at a non-scheduled visit. • The date of the latest scheduled visit if the subject is terminated early from study at a scheduled visit or lost to follow-up.
Age (Years) at EFP Symptom Onset	Date of EFP symptoms reported – Date of Birth/365.25. See Section 6.3.1.3 for handling of partial or unknown EFP symptom onset dates.
Time (Years) since last EFP treatment	Date of most recent EFP treatment – Date of informed consent/365.25. See Section 6.3.1.3 for handling of partial or unknown EFP treatment dates.
Baseline CR-PCSS Buttock Score	Investigator baseline CR-PCSS scores for each buttock will be based on the investigator's CR-PCSS evaluation done at the Screening Visit.
Duration (Minutes) of Exposure at each visit	Date/Time of Last Injection – Date/Time of First Injection
Duration (Days) of AE	AE end date – AE start date + 1
AE Onset Day	AE start date – Date of first injection + 1

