5.4. Screen Failures

Screen failures are defined as subjects who consent to participate in this study but are not subsequently treated. Eligibility confirmation by the sponsor or designee is required for this study (see Section 8.1).

Subjects will be allowed to repeat any single screening assessment/procedure once, if necessary, if it is within the screening window. The subject will not be considered a screen failure unless the repeat assessment/procedure result does not meet eligibility criteria. The period from the start of screening related procedures at the Screening Visit to the Day 1 Visit must not exceed 28 days, inclusive of any repeat screening procedures.

Subjects who do not meet all of the eligibility criteria at the Screening or Day 1 Visits will be deemed a screen failure and the following information must be recorded for all subjects who are screen failures:

- Demography (age, gender, race/ethnicity).
- Reason for screen failure.
- Which eligibility criterion was not met.
- Any AEs (including serious adverse events [SAEs]) experienced by the subject.

A subject who is a screen failure at the Screening Visit may be rescreened with approval from the sponsor. The subject must repeat all screening procedures. The period from the start of rescreening related procedures to the study treatment must not exceed 28 days. Subjects may be rescreened only once; however subjects whose rescreening process was interrupted by COVID-19 may be rescreened for a second time.

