4.5. Prior EFP Treatment

Prior EFP treatment will be obtained from the prior/concomitant medication and/or prior/concomitant procedure pages of the eCRF. If on either of these pages a medication or procedure is reported with the indication ‘EFP/Cellulite’ prior to the Screening Visit, then the medication or procedure will be considered a prior EFP treatment.

All EFP treatment medications will be classified as EFP Drug. All EFP treatment procedures will be classified into one of the following groups:

- Liposuction.
- Surgery (including subcision and/or powered subcision).
- Laser.
- Massage.
- Radiofrequency.
- Mesotherapy.
- Cream.
- Other.

The classification will be reviewed and approved by the study medical monitor. Any EFP treatment used after the Day 1 visit will be noted and reported as a protocol deviation.

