6.3.1.3. Missing EFP Onset Date

Missing EFP onset days will be imputed with the first day of the month and missing onset month will be imputed with January. If the EFP onset date is indicated as completely unknown but starting less than 5 years ago, the EFP onset date will be imputed as the informed consent date minus 5 years. If the EFP onset date is indicated as completely unknown but starting more than 5 years ago, the EFP onset date will not be imputed. Missing EFP medication/treatment end days will be imputed with the last day of the month and missing end months will be imputed with December, except if the end year is equal to the date of injection year and then the EFP medication/treatment end date will be imputed with the first injection date.

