6.3.1.4. Missing Last Menstrual Date

Missing date of last menstrual period will be imputed with the last day of the month and missing onset month will be imputed with December.

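### SAP date rules give negative or impossible values for time since last EFP treatment and time since last menstrual period; descriptive tables only

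*SAP*

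**What the plan says.** SAP 6.2, Table 18, gives the time in years since the last EFP treatment as "Date of most recent EFP treatment – Date of informed consent/365.25" and refers to SAP 6.3.1.3 for partial dates. The age-at-onset row has the same layout but runs from later to earlier: "Date of EFP symptoms reported – Date of Birth/365.25".

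SAP 4.5 fixes which treatments count. One reported with the EFP indication "prior to the Screening Visit, then the medication or procedure will be considered a prior EFP treatment".

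SAP 6.3.1.3 has a general rule for partial end dates: "Missing EFP medication/treatment end days will be imputed with the last day of the month and missing end months will be imputed with December". An exception follows: "except if the end year is equal to the date of injection year and then the EFP medication/treatment end date will be imputed with the" date of first injection. SAP 6.3.1.4 says that a missing last menstrual date is "imputed with the last day of the month and missing onset month will be imputed with December". Neither section sets an upper limit at consent or Screening.

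On timing, Protocol 5.4 states: "The period from the start of screening related procedures at the Screening Visit to the Day 1 Visit must not exceed 28 days". The Schedule of Activities puts Screening at Day -28 to Day -1, with consent before any other study assessment. Protocol 8.3.1 collects the last menstrual date at the Screening Visit.

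Both variables are reported. SAP 7.5 summarises time since the most recent EFP treatment by cohort and overall. SAP 7.3 summarises time since last menstrual period as a continuous baseline variable.

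**The concern.** A time-since variable should be zero or positive. Table 18 subtracts the later date from the earlier one, so its sign is reversed. The partial-date rules can also place an event after the visit at which it was reported as already past. That is impossible for a prior treatment as SAP 4.5 defines it, and impossible for a menstrual date taken at Screening.

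These are derivation rules that a programmer is expected to follow, and they stand in SAP version 2.0. What is at stake is the credibility of a few descriptive rows. Means and ranges of time since last EFP treatment would mix two signs, and one menstrual value of several hundred negative days could pull a cohort mean or minimum.

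**Working it through.** The plan gives no figure to reproduce. The dates below are illustrations within the study period. Consent is taken to fall on the day Screening starts, so first injection is 1 to 28 days after consent. The Table 18 formula is read with the brackets it evidently intends: (treatment date - consent date)/365.25.

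**Step 1: sign, fully dated treatments.**
- Treatment 15 June 2018, consent 10 February 2020: -605/365.25 = -1.656 years.
- Treatment 10 February 2019, same consent: -365/365.25 = -0.999 years.
- Reversing the subtraction gives +1.656 and +0.999.

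**Step 2: partial EFP end dates.**

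| Recorded end | Consent | First injection | Rule | Imputed end | Days after consent | Table 18 (years) | Formula reversed (years) |
|---|---|---|---|---|---|---|---|
| 2020 | 10 Feb 2020 | 9 Mar 2020 | exception | 9 Mar 2020 | 28 | +0.077 | -0.077 |
| 2020 | 10 Feb 2020 | 11 Feb 2020 | exception | 11 Feb 2020 | 1 | +0.003 | -0.003 |
| 2019 | 10 Dec 2019 | 7 Jan 2020 | general | 31 Dec 2019 | 21 | +0.057 | -0.057 |
| Dec 2019 | 20 Dec 2019 | 7 Jan 2020 | general | 31 Dec 2019 | 11 | +0.030 | -0.030 |

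The first two rows show the exception passing consent at both ends of the screening window. The last two show that the general rule can pass it too. Under Table 18 as written these values are positive while fully dated ones are negative. Under the reversed formula the pattern flips. The sign and the upper limit therefore both need correcting.

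**Step 3: a known month in the injection year.** Take consent on 10 February 2020 and injection on 9 March 2020.
- If the exception covers any partial date, an end recorded as January 2020 becomes 9 March 2020, 28 days after consent.
- If it covers only a missing month, January 2020 becomes 31 January 2020, 10 days before consent, which is sensible. An end recorded as February 2020 still becomes 29 February 2020, 19 days after consent.

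The wording does not settle which is meant. A limit is needed on either reading.

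**Step 4: last menstrual date.** Table 18 has no formula for this variable; here it is Screening date minus imputed date.
- Screening 10 February 2020, recorded February 2020: imputed 29 February 2020, -19 days.
- Same Screening, recorded 2020: imputed 31 December 2020, -325 days.
- Screening 1 November 2019, recorded 2019: imputed 31 December 2019, -60 days.
- Screening 10 February 2020, recorded January 2020 or 2019: +10 and +41 days, so earlier partial dates cause no problem.

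**Step 5: after the repair.** With the formula reversed and end dates limited to consent, the four rows of Step 2 become 0. January 2020 with the month kept gives 10/365.25 = +0.027 years. With menstrual dates limited to Screening, -19, -325 and -60 days become 0, and +10 and +41 are unchanged.

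**The case against.** The best reply is that this is a drafting slip. The variable's name fixes the intended direction, negative times would be obvious in output, and only descriptive rows are touched. That is fair on importance, but it does not make the rules workable: a programmer who simply flips the sign still gets negative values for the imputed dates.

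The missing brackets are a weaker complaint. The age-at-onset row has the same form, so they are probably shorthand, and layout may have been lost in reading the PDF. The reversed order is the real error.

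Four stronger readings are tempting, and the documents do not support them:

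- *Every value has the wrong sign.* This fails for dates imputed past consent, which come out positive.
- *A known month is overwritten.* The exception directly follows the clause on missing months and may qualify only that clause. The text is ambiguous.
- *Compliant subjects will appear to breach the washouts in exclusion 8.* The injection-date exception applies only to treatments ending in the injection year. Those are less than 12 months before injection, so the 12-month items (8a to 8c) are already breached on the true date. Only the 6-month, 3-month and 2-week items could be affected. Even then, SAP 4.3 draws deviations from eCRF data, vendor data and monitoring reports, with study-team review, and does not say that imputed dates feed it.
- *A stated share of menstrual dates will fall after Screening.* Any such share depends on an assumed distribution of recent periods. Inclusion criterion 6 also admits postmenopausal women and women with a hysterectomy, whose last period may be years back and would not be pushed past Screening.

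**Conclusion.** The point holds as a minor correction. As written, Table 18 gives a negative time for every fully dated prior EFP treatment. SAP 6.3.1.3 can date a prior treatment after consent, by 1 to 28 days under the injection-year exception, with the opposite sign from the fully dated treatments. SAP 6.3.1.4 can place a recent partial menstrual date after the visit at which it was collected. No other section of either document corrects the sign or limits these dates.

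The size in the study cannot be stated, because the documents do not say how many dates are partial. The 1 to 28 day range assumes consent on the day Screening starts, and the worked values rest on illustrative dates. The effect is confined to the EFP-history and baseline summaries and any listings of these derived values. The primary and secondary efficacy endpoints, the analysis populations and the safety conclusions are unaffected.

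**What to change.** Four short changes to SAP text:

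1. Table 18, time since last EFP treatment: (date of informed consent - date of most recent EFP treatment)/365.25.
2. Table 18, age at onset: (date of EFP symptom onset - date of birth)/365.25. The brackets are for clarity only.
3. SAP 6.3.1.3: keep a known month; impute a missing day to the last day of the month and a missing month to December; then take the earlier of that date and the informed consent date. This replaces the injection-year exception.
4. SAP 6.3.1.4: same rule, taking the earlier of the imputed date and the Screening date. It would help to add the missing Table 18 line for time since last menstrual period, measured back from Screening.

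The limits remove impossible values but do not recover the true date: a capped record contributes a time of zero. A footnote with the number of imputed and capped dates would let readers judge how far the summaries depend on them. The cost is a few lines of text and the matching program code, with no new data.
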